9.3.2. Outcomes

When available, the following variables will be collected after initiation of Mysimba/Contrave (Post-Index Date). A draft listing of variables available in each country is included in Appendix 3 and will be included as final in the Statistical Analysis Plan (SAP).

Proprietary and Confidential:

This document cannot be used, distributed, or reproduced in any way without the prior written consent of Currax Pharmaceuticals LLC.

- 1. BMI, height, and weight prior to index date, the date of initiation of the medication(s) of interest, (obtained directly from data sources; BMI may be calculated if height and weight available). In the event that BMI and/or weight are not available through licensed access to the Scandinavian National Patient Registries, an attempt will be made to identify the obese population through diagnosis codes or procedures such as counseling for weight loss. It should be noted that this approach may identify a more obese and more motivated population than what would be identified on the basis of BMI. In addition, an approach may be implemented to predict BMI or apply published algorithms predicting BMI. Details will be laid out in the SAP.
- 2. Weight will be obtained if available 16-24 weeks post-index date to evaluate use inconsistent with labelled indication. BMI after index date will be obtained in the same timeframe, if available.
- 3. Relevant comorbidities (obtained via ICD-10 codes):
 - 1. Weight-related comorbidities (i.e., type 2 diabetes, dyslipidaemia, hypertension)
 - 2. Neuropsychiatric conditions (mania, bipolar disorder, major depressive disorder [MDD], anorexia nervosa, bulimia)
 - 3. Uncontrolled hypertension
 - 4. Moderate or severe renal impairment
 - 5. End-stage renal disease
 - 6. Seizure disorder
 - 7. Hepatic impairment (defined by Child-Pugh score category)
 - 8. Central nervous system tumour
- 4. Concomitant medication use, including: naltrexone, bupropion, CYP2B6 inhibitors, CYP2B6 inducers, CYP2B6 substrates, CYP2D6 substrates, drugs that lower seizure threshold, opioid or opiate agonist, or MAOI (obtained via ATC [outpatient, Nordic data] or NDC [US data])
- 5. Pregnancy status and breastfeeding status (obtained via ICD-10 codes)
- 6. AESIs (obtained via ICD-10 codes):
 - 1. Seizures

- 2. Suicidality (i.e., suicidal ideation, attempted suicide or completed suicide)
- 3. Neuropsychiatric events (i.e., mania or depression)
- 4. Hepatotoxicity
- 5. Severe hypersensitivity reaction

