Name of the main author of the protocol.				
Name of the main author of the protocol:				
Date: dd/Month/year				
Signature:				

15. Appendix 2. Code lists

Mysimba ATC: A08AA62 Contrave NDC: search terms – Contrave, naltrexone, bupropion Naltrexone ATC: N07BB04, A06AH01, N02AA56	
Contrave NDC: search terms – Contrave, naltrexone, bupropion	
Naltrexone ATC: N07BB04, A06AH01, N02AA56	
NDC: search terms – naltrexone	
Bupropion ATC: N06AX12	
NDC: search terms – bupropion	
Concomitant Medications	
CYP2B6 inhibitors See Appendix 2A	
CYP2B6 inducers See Appendix 2A	
CYP2B6 substrates See Appendix 2A	
CYP2D6 substrates See Appendix 2A	
Drugs that lower Propoxyphene, remifentanil, sufentanil, tapentadol, tramadol,	
seizure threshold baclofen, buspirone, dalfampridine, lithium, mefenamic acid,	
amphetamine, benzphetamine hydrocholoride, dextroamphetan	mine,
hydroxyamphetamine hydrobromide, lisdexamfetamine dimes	
methamphetamine hydrochloride, cocaine, phenylpropanolam	
dexamphetamine, methylphenidate	
Opioid or opiate ATC: N02A;	
agonist	
Opium alkaloids & ATC: R05DA, N02AA	
derivatives	
MAOI ATC: N04BD, N06AF, N06AG	
Seizures ICD-10: G40	
Increase in blood ICD-10: R00.0, R03.0	
pressure or heart rate	
Hypersensitivity, ICD-10: T78, L51	
including Stevens-	
Johnson	
Serotonin syndrome ICD-10: T43.225A	
Suicidality ICD-10: R45.851, T14.91	
Diabetes ICD-10: E10-E11	
Dyslipidaemia ICD-10: E78	
Neuropsychiatric	
conditions:	
Mania ICD-10: F30	
Bipolar disorder ICD-10: F31	

N4 : 1 :	ICD 10 F22
Major depressive	ICD-10: F33
disorder	ICD 10 F50 0
Anorexia nervosa	ICD-10: F50.0
Bulimia	ICD-10: F50.2
Hypertension	ICD-10: I10-I16
TT . 11 1	
Uncontrolled	ICD-10: I10-I16 (with Systolic ≥140 mmHg or diastolic ≥90 mmHg)
hypertension	10D 10 N10 0 N10 5
Moderate or severe	ICD-10: N18.3-N18.5
renal impairment	
End stage renal	ICD-10: N18.6
disease	
Hepatic impairment	ICD-10: K70, K72-K75
Central nervous	ICD-10: C72
system tumour	
Substance	ICD-10: F10-F19
abuse/dependency	
	ATC: N06AA11
Protriptyline*	NDC: search terms – protriptyline
Dannanidal (Anarril)*	ATC: N05AD07
Benperidol (Anquil)*	No NDC
Flupentixol	ATC N05AF01
(Depixol)*	No NDC
Fluphenazine	ATC: N05AF02
(Modecate,	NDC: search terms – fluphenazine
Prolixin)*	•
Levomepromazine	ATC: N05AA02
(Nozinan)*	No NDC
Loxapine	ATC: N05AH01
(Loxitane)*	NDC: search terms – loxapine
	ATC: N05AE02
Molindone (Moban)*	NDC: search terms – molindone
	ATC: N05AC01
Periciazine*	No NDC
Sulpiride (Dolmatil,	ATC: N05AL01
Sulpor)*	No NDC

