Methylphenobarbital	No NDC
Methyltestosterone	ATC: G03BA02, G03EK01, G03EA01
Methyltestosterone	ATC: GU3BAU2, GU3EKUI, GU3EAUI

	NDC: search terms- methyltestosterone
	ATC: G03FA13, G03AA11, G03AB09
Norgestimate	NDC: search terms- norgestimate
	ATC: G03XC05
Ospemifene	NDC: search terms- ospemifene
	ATC: B01AC22
Prasugrel	NDC: search terms- prasugrel
	ATC: V03AB05, D04AA10, R06AD02, R06AD52
Promethazine	NDC: search terms- promethazine
	ATC: N01AX10
Propofol	NDC: search terms- propofol
•	ATC: L01XH02
Romidepsin	NDC: search terms- romidepsin
	ATC: N01BB09
Ropivacaine	NDC: search terms- ropivacaine
	ATC: R03DX06
Seratrodast	No NDC
	ATC: N01AB08
Sevoflurane	NDC: search terms- sevoflurane
	ATC: N05CD07
Temazepam	NDC: search terms- temazepam
	ATC: G03BA03, G03EA02
Testosterone	NDC: search terms- testosterone
	ATC: D10AD01, L01XF01, D10AD51
Tretinoin	NDC: search terms- tretinoin
	ATC: D10AD06
Trifarotene	NDC: search terms- trifarotene
	ATC: N03AG01
Valproic acid	NDC: search terms- valproic acid
	ATC: J05AP55, J05AP56
Velpatasvir	NDC: search terms- velpatasvir
	ATC: C09BB10, C08DA01, C08DA51
Verapamil	NDC: search terms- verapamil
	ATC: B06AX03
Voxelotor	NDC: search terms- voxelotor
	ATC: L01EL03
Zanubrutinib	NDC: search terms- zanubrutinib
	ATC: C07AB04, C07BB04
Acebutolol	NDC: search terms- acebutolol
	No ATC
Acetaminophen	NDC: search terms- acetaminophen
	ATC: N02CC05
Almotriptan	NDC: search terms- almotriptan
A.1 . 11 . 1	ATC: A10BH04, A10BD13, A10BD09
Alogliptin	NDC: search terms- alogliptin

	ATC: C07AA01
Alprenolol	No NDC
ruprenoioi	ATC: N02BB03, N02BB53, N02BB73
Aminophenazone	No NDC
7 mmophenazone	ATC: N06AA17
Amoxapine	NDC: search terms- amoxapine
Ашохарше	No ATC
Amphetamine	NDC: search terms- amphetamine
Ampliciamine	ATC: J05AE05
Ampropovir	No NDC
Amprenavir	ATC: C01BB04
Ai 4i	
Aprindine	No NDC
AC 1	No ATC
Arformoterol	NDC: search terms- arformoterol
A · · 1	ATC: N05AX12
Aripiprazole	NDC: search terms- aripiprazole
	ATC: N05AH05
Asenapine	NDC: search terms- asenapine
	ATC: R06AX11
Astemizole	No NDC
	ATC: J05AP06, J05AP58
Asunaprevir	No NDC
	ATC: C07AB03, C07FB03, C07CB53, C07BB03, C07DB01
Atenolol	NDC: search terms- atenolol
	ATC: N06BA09
Atomoxetine	NDC: search terms- atomoxetine
	ATC: R01AC03, R06AX19, S01GX07
Azelastine	NDC: search terms- azelastine
	ATC: S01ED06
Befunolol	No NDC
	ATC: L04AA48
Belumosudil	NDC: search terms- belumosudil
	ATC: N04AC01
Benzatropine	No NDC
	ATC: P03AX06
Benzyl alcohol	NDC: search terms- benzyl alcohol
	ATC: C08EA02

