Desipramine	NDC: search terms- desipramine
1	ATC: N07XX16
Deutetrabenazine	NDC: search terms- deutetrabenazine
	ATC: R06AB02, R06AB52
Dexchlorpheniramine	NDC: search terms- dexchlorpheniramine
	ATC: A08AA04
Dexfenfluramine	No NDC
	No ATC
Dextroamphetamine	NDC: search terms- dextroamphetamine
	ATC: R05DA09, N07XX59
Dextromethorphan	NDC: search terms- dextromethorphan
_	ATC: N02AC04, N02AC54, N02AC74
Dextropropoxyphene	No NDC
	ATC: N02AA08, N02AJ02, N02AJ03, N02AJ01, N02AA58
Dihydrocodeine	NDC: search terms- dihydrocodeine
	ATC: C05AE03, C08DB01
Diltiazem	NDC: search terms- diltiazem
	ATC: D04AA32, R06AA02, D04AA33, R06AA52
Diphenhydramine	NDC: search terms- diphenhydramine
	ATC: A04AA04
Dolasetron	NDC: search terms- dolasetron

	ATC: N06DA02, N06DA52, N06DA53
Donepezil	NDC: search terms- donepezil
Вопереди	ATC: N06AA16
Dosulepin	No NDC
Возитерии	ATC: C02CA04
Doxazosin	NDC: search terms- doxazosin
BOMBEOSIII	ATC: D04AX01, N06AA12
Doxepin	NDC: search terms- doxepin
Волерін	ATC: C01BD07
Dronedarone	NDC: search terms- dronedarone
Bronedarone	ATC: N06AX21
Duloxetine	NDC: search terms- duloxetine
Burelletine	ATC: H01CC03
Elagolix	NDC: search terms- elagolix
	ATC: N02CC06
Eletriptan	NDC: search terms- eletriptan
	ATC: A16AX10
Eliglustat	NDC: search terms- eliglustat
211310001001	ATC: C01BC08
Encainide	No NDC
	ATC: L01EC03
Encorafenib	NDC: search terms- encorafenib
	ATC: C07AB10
Epanolol	No NDC
	ATC: R06AX24, S01GX10
Epinastine	NDC: search terms- epinastine
	ATC: L01EB02
Erlotinib	NDC: search terms- erlotinib
	ATC: N06AB10
Escitalopram	NDC: search terms- escitalopram
	ATC: C07AB09
Esmolol	NDC: search terms- esmolol
	ATC: R05DA01, S01XA06
Ethylmorphine	No NDC
 	ATC: A08AA02, N03AX26
Fenfluramine	NDC: search terms- fenfluramine
	ATC: G04BD11
Fesoterodine	NDC: search terms- fesoterodine
	ATC: C01BC04
Flecainide	NDC: search terms- flecainide
	ATC: N07CA03
Flunarizine	No NDC
	ATC: N06AB03, N06CA03
Fluoxetine	NDC: search terms- fluoxetine
Fluvastatin	ATC: C10AA04
	•

	NDC: search terms- fluvastatin
	ATC: N06AB08
Fluvoxamine	NDC: search terms- fluvoxamine
T TO	ATC: R03AC13, R03CC15, R03AL05, R03AK08, R03AK07,
	R03AK11, R03AL07, R03AK09, R03AL10, R03AL09, R03AL11
Formoterol	NDC: search terms- formoterol
Fusidic acid	ATC: D06AX01, D09AA02, J01XC01, S01AA13
(Fucidin)	NDC: search terms- fucidin
(Fucialii)	ATC: N06DA04
Galantamine	NDC: search terms- galantamine
Galalitallille	ATC: L01EB01
Gefitinib	
Genunio	NDC: search terms- gefitinib

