	ATC: R03AL07, R03AL09, R03AL11, D11AA01, A03AB02,
	R03BB06, A03CA05, R03AL04, R03AL12
Glycopyrronium	NDC: search terms- glycopurronium
TT 1 '1 1	ATC: N05AD01
Haloperidol	NDC: search terms- haloperidol
TT 1 11 .	ATC: P01BA02
Hydroxychloroquine	NDC: search terms- hydrochloroquine
	ATC: L01EL01
Ibrutinib	NDC: search terms- ibrutinib
	ATC: L01DB06
Idarubicin	NDC: search terms- idarubicin
	ATC: N05AX14
Iloperidone	NDC: search terms- iloperidone
	ATC: L01EA01
Imatinib	NDC: search terms- imatinib
	ATC: N06AA02, N06AA03
Imipramine	NDC: search terms- imipramine
	No ATC
Indenolol	NDC: search terms- indenolol
	No ATC
Ipecac	NDC: search terms- ipecac
	ATC: N04CX01
Istradefylline	NDC: search terms- istradefylline
	ATC: D11AX22, P02CF01
Ivermectin	NDC: search terms- ivermectin
	ATC: L01XG03
Ixazomib	NDC: search terms- ixazomib
	ATC: C07AG01, C07CG01, C07BG01
Labetalol	NDC: search terms- labetalol
	ATC: C07AB14
Landiolol	No NDC
	ATC: J05AX18
Letermovir	NDC: search terms- letermovir

	ATC: S01ED03
Levobunolol	NDC: search terms- levobunolol
Levocanoror	ATC: N06AX28
Levomilnacipran	NDC: search terms- levomilnacipran
 Le vommuerprun	ATC: C01BB01, C05AD01, D04AB01, N01BB02, R02AD02,
	S01HA07, S02DA01, N01BB52
Lidocaine	NDC: search terms- lidocaine
210000000	ATC: N06BA12
Lisdexamfetamine	NDC: search terms- lisdexamfetamine
 	ATC: G02CB02, N02CA07
Lisuride	No NDC
	ATC: N07BC04
Lofexidine	NDC: search terms- lofexidine
	ATC: A07DA03, A07DA05, A07DA53
Loperamide	NDC: search terms- loperamide
•	ATC: R06AX13
Loratadine	NDC: search terms- loratadine
	ATC: A08AA11
Lorcaserin	NDC: search terms- lorcaserin
	ATC: A07DA03, A07DA03, A07DA53
Lorpiprazole	No NDC
•	ATC: N06AA21
Maprotiline	No NDC
	No ATC
Meclizine	NDC: search terms- meclizine
	No ATC
Meperidine	NDC: search terms- meperidine
1	ATC: N03AB04, N03AB54
Mephenytoin	No NDC
•	ATC: C07AA14
Mepindolol	No NDC
	ATC: R06AD07
Mequitazine	No NDC
	ATC: N05AC03
Mesoridazine	No NDC
	ATC: N06BA03
Metamfetamine	No NDC
	ATC: N02BG09
Methoxyflurane	No NDC
	No ATC
Methylene blue	NDC: search terms- methylene blue
	ATC: S01ED04, C07BA68, S01ED54
Metipranolol	No NDC
	ATC: A03FA01
Metoclopramide	NDC: search terms- metoclopramide

Metoprolol		ATC: C07AB02, C07FX03, C07FB13, C07FB02, C07FX05,

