Nicotine NDC: search terms- nicotine ATC: C07FB03, C08CA05, C08GA01, C08CA55 Nifedipine NDC: search terms- nifedipine ATC: N06AA10 Nortriptyline NDC: search terms- nortiptyline ATC: N05AH03	Nicergonne	
ATC: C07FB03, C08CA05, C08GA01, C08CA55 NDC: search terms- nifedipine ATC: N06AA10 Nortriptyline NDC: search terms- nortiptyline ATC: N05AH03	Nicotino	
Nifedipine NDC: search terms- nifedipine ATC: N06AA10 Nortriptyline NDC: search terms- nortiptyline ATC: N05AH03	Nicotific	
ATC: N06AA10 Nortriptyline NDC: search terms- nortiptyline ATC: N05AH03	N: 6. 4:	
Nortriptyline NDC: search terms- nortiptyline ATC: N05AH03	Niledipine	1
ATC: N05AH03	NT 4 1 4 11	
	Nortriptyline	
	01 .	
Olanzapine NDC: search terms- olanzapine	Olanzapine	
ATC: N02AX07	01' '1'	
Oliceridine NDC: search terms- oliceridine	Oliceridine	
ATC: A04AA01		
Ondansetron NDC: search terms- ondansetron	Ondansetron	
ATC: H02CA02		
Osilodrostat NDC: search terms- osilodrostat	Osilodrostat	NDC: search terms- osilodrostat

	ATC: P02BA02
Oxamniquine	No NDC
- Chairminguine	ATC: C07AA02, C07AC02, C07BA02
Oxprenolol	No NDC
	ATC: N05AX13
Paliperidone	NDC: search terms- paliperidone
1 00110 0110	ATC: A04AA05, A04AA55
Palonosetron	NDC: search terms- palonosetron
	ATC: N06AB05
Paroxetine	NDC: search terms- paroxetine
	ATC: L01EX03
Pazopanib	NDC: search terms- pazopanib
	ATC: C07AA23, C07CA23
Penbutolol	No NDC
	ATC: P01CX01
Pentamidine	NDC: search terms- pentamidine
	ATC: C08EX02
Perhexiline	No NDC
	ATC: N05AB03
Perphenazine	No NDC
	ATC: N02BE03, N02BE73
Phenacetin	NDC: search terms- phenacetin
	ATC: A10BA01, A10BD01
Phenformin	No NDC
	ATC: N03AB04, N03AB52
Phenytoin	NDC: search terms- phenytoin
	ATC: N05AX17
Pimavanserin	NDC: search terms- pimavanserin
	ATC: N05AG02
Pimozide	NDC: search terms- pimozide
	ATC: C07AA03
Pindolol	NDC: search terms- pindolol
	ATC: P02CB01
Piperazine	NDC: search terms- piperazine
	ATC: N05AC04
Pipotiazine	No NDC
	ATC: L04AX05
Pirfenidone	NDC: search terms- pirfenidone
	ATC: L01EA05
Ponatinib	NDC: search terms- ponatinib
	ATC: C07AB01
Practolol	No NDC
	ATC: L01EX23
Pralsetinib	NDC: search terms- pralsetinib
Procainamide	ATC: C01BA02

	NDC: search terms- procainamide
	ATC: N05AB04
Prochlorperazine	NDC: search terms- prochlorperazine
Trochiorperazine	ATC: G03DA04, G03FA04
Progesterone	NDC: search terms- progesterone
Progesterone	ATC: N05AA03
D .	
Promazine	NDC: search terms- promazine
D 1	ATC: N02BE05
Propacetamol	No NDC
	ATC: C01BC03
Propafenone	NDC: search terms- propafenone

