Pentamidine	
Perhexiline	
Perospirone	
Perphenazine	
Phenacetin	
Phenformin	
Phenytoin	
Pimavanserin	
Pimozide	
Pindolol	
Piperazine	
Pipotiazine	
Pirfenidone	
Pitolisant	
Ponatinib	
Practolol	
Pralsetinib	
Procainamide	
Prochlorperazine	
Progesterone	
Promazine	
Promethazine	
Propacetamol	
Propafenone	

Propranolol
Quetiapine
Quinine
Ranolazine
Remdesivir
Remoxipride
Repinotan
Revefenacin
Ripretinib
Risperidone
Ritonavir
Rotigotine
Rucaparib
Rupatadine
Selegiline
Sertindole
Sertificitie
Sertraine
Simvastatin
Solifenacin
Sotalol
Sparteine
Tafenoquine
Talinolol
Tamoxifen
Tamsulosin
Tapentadol
Tapinarof
Tegaserod
Terfenadine
Tertatolol
Tesmilifene
Tetrabenazine
Theophylline
Thioridazine
Ticlopidine
Timolol
Tiotropium
Tipranavir
Tolterodine
Trabectedin
Tramadol
Trazodone
Triclabendazole
Trimipramine
Umeclidinium
Umifenovir
Upadacitinib
Valbenazine
Venlafaxine
Vernakalant
Vilazodone
Viloxazine
Vortioxetine
Yohimbine
Zolpidem
Zuclopenthixol
Zaciopericiixoi

Opioids

Acetaminophen/Caffeine/Dihvdrocodeine bitartrate

Acetaminophen/Codeine Phosphate

Acetaminophen/Oxycodone Hydrochloride

alfentanil

Alfentanil Hydrochloride

Aspirin/Caffeine/Dihydrocodeine Bitartrate

Aspirin/Codeine Phosphate

Aspirin/Oxycodone Hydrochloride

Belladonna/Opium

Benzhydrocodone/Acetaminophen

bezitramide

Buprenorphine

Buprenorphine Hydrochloride

Buprenorphine/Naloxone

Butalbital/Acetaminophen/Caffeine/Codeine Phosphate

Butalbital/Aspirin/Caffeine/Codeine Phosphate

Butorphanol Tartrate

butorphanol

Carisoprodol/Aspirin/Codeine Phosphate

Celecoxib/Tramadol Hydrochloride

Chlorpheniramine Polistirex/Codeine Polistirex

codeine

codeine and acetylsalicylic acid

codeine and ibuprofen

codeine and other non-opioid analgesics

codeine and paracetamol

Codeine Phosphate/Guaifenesin

Codeine Sulfate

codeine, combinations excl. psycholeptics

codeine, combinations with psycholeptics

dextromoramide

dextropropoxyphene

dextropropoxyphene, combinations excl. psycholeptics

dextropropoxyphene, combinations with psycholeptics

dezocine

Difelikefalin

Difenoxin Hydrochloride/Atropine Sulfate

dihydrocodeine and acetylsalicylic acid

dihydrocodeine and other non-opioid analgesics

dihydrocodeine and paracetamol

dihydrocodeine

dihydrocodeine, combinations

Diphenoxylate Hydrochloride/Atropine Sulfate

Fentanyl Citrate

fentanyl

FENTANYL/DROPERIDOL

hydrocodone

Hydrocodone Bitartrate

Hydrocodone Bitartrate/Acetaminophen

Hydrocodone Bitartrate/Chlorpheniramine Maleate

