Hydrocodone bitartrate/Guaifenesin

Hydrocodone Bitartrate/Homatropine Methylbromide

Hydrocodone Bitartrate/Ibuprofen

Hydrocodone bitartrate/Pseudoephedrine Hydrochloride

Hydrocodone Polistirex/Chlorpheniramine Polistirex

Hydrocodone/Chlorpheniramine/Pseudoephedrine

Hydrocodone/Pseudoephedrine/Guaifenesin

hydromorphone hydromorphone and antispasmodics hydromorphone and naloxone Hydromorphone Hydrochloride hydromorphone ketobemidone and antispasmodics ketobemidone LEVOMETHADYL **LEVORPHANOL** Levorphanol Tartrate meperidine Meperidine Hydrochloride Meperidine Hydrochloride/Promethazine Hydrochloride meptazinol methadone Methadone Hydrochloride methadone, combinations excl. psycholeptics morphine and antispasmodics Morphine Sulfate Morphine Sulfate Liposome Morphine Sulfate/Naltrexone Hydrochloride morphine morphine, combinations Nalbuphine Hydrochloride nalbuphine nicomorphine oliceridine opium oxycodone and acetylsalicylic acid oxycodone and ibuprofen oxycodone and naloxone oxycodone and naltrexone oxycodone and paracetamol Oxycodone Hydrochloride Oxycodone Hydrochloride/Naloxone Hydrochloride Oxycodone Hydrochloride/Naltrexone Hydrochloride oxycodone Oxycodone/Ibuprofen Oxymorphone Hydrochloride oxymorphone papaveretum Paregoric pentazocine pethidine and antispasmodics pethidine pethidine, combinations excl. psycholeptics pethidine, combinations with psycholeptics phenazocine piritramide Promethazine Hydrochloride/Codeine Phosphate Promethazine/Phenylephrine/Codeine Phosphate **PROPOXYPHENE** PROPOXYPHENE NAPSYLATE/ACETAMINOPHEN remifentanil Remifentanil Hydrochloride sufentanil Sufentanil Citrate Tapentadol Hydrochloride

tapentadol
tilidine and naloxone
tilidine
tramadol and celecoxib
tramadol and dexketoprofen
tramadol and other non-opioid analgesics
tramadol and paracetamol
Tramadol Hydrochloride
Tramadol Hydrochloride/Acetaminophen
tramadol

Triprolidine/Pseudoephedrine/Codeine

Opium alkaloid and derivatives

ATC: R05A

acetyldihydrocodeine codeine combinations dextromethorphan dimemorfan ethylmorphine hydrocodone normethadone noscapine opium alkaloids with morphine pholcodine thebacon

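### Appendix 2 gives no ATC code for paracetamol, pethidine and two amphetamines, and gives phenytoin the mephenytoin code, so Nordic co-medication counts would be understated

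*Protocol*

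**What the plan says.** Section 9.3.2 (item 4) says concomitant medication is "obtained via ATC [outpatient, Nordic data] or NDC [US data". Section 9.3.3 uses the same rule for prior medication and points to Appendix 2 and 2a. Section 9.3.2 also makes the Appendix 2 code lists the pre-specified definitions from which all variables are identified.

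Four rows of Appendix 2 read 'No ATC' and give only a US search term:
- acetaminophen: "NDC: search terms- acetaminophen"
- amphetamine, in the same form
- dextroamphetamine: "NDC: search terms- dextroamphetamine"
- meperidine: "NDC: search terms- meperidine"

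The phenytoin row reads "ATC: N03AB04, N03AB52". The mephenytoin row lists N03AB04 and N03AB54.

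The row for drugs that lower the seizure threshold gives drug names (for example "amphetamine, benzphetamine hydrocholoride") and no codes of either kind.

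Appendix 3 marks use of CYP2B6 inducers, CYP2B6 substrates, CYP2D6 substrates and seizure-threshold drugs as 'Yes' in all four Nordic countries.

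**The concern.** A 'No ATC' entry tells the Nordic analyst that there is nothing to search for. If a code exists and the blank came from looking up a US drug name, users of that drug go unflagged in every Nordic registry. A wrong code does the same and also puts other patients into the wrong drug row.

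Section 9.3.3 lists CYP2B6, CYP2D6 and seizure-threshold medication among the baseline variables, and primary objective 1 is to describe baseline characteristics. Section 9.7.3.1 uses concomitant medication again, in the subgroup incidence of adverse events of special interest (AESIs) and in the incidence of new co-medication. The errors therefore reach reported results, and Appendix 3 gives no warning of them.

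**Working it through.** The protocol states no figure to reproduce. The check compares rows of the document with each other.

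**1. The 'No ATC' rows**

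| Appendix 2 row | Other name in the protocol | Coded relatives in Appendix 2 | Class in Appendix 2a |
|---|---|---|---|
| Acetaminophen | paracetamol, only inside opioid combinations such as "codeine and paracetamol" (Appendix 2a) | phenacetin N02BE03, propacetamol N02BE05 | CYP2D6 |
| Meperidine | pethidine, e.g. "pethidine, combinations excl. psycholeptics" (Appendix 2a) | ketobemidone N02AB01 | CYP2B6 substrate, CYP2D6 |
| Dextroamphetamine | dexamphetamine (seizure-threshold row) | metamfetamine N06BA03, lisdexamfetamine N06BA12 | CYP2D6 |
| Amphetamine | none found | as above | CYP2D6 |

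That the paired names are synonyms is ordinary drug nomenclature; the protocol does not state it. Two rows show the same thing in the other direction. Rifampicin has 'No NDC', though Appendix 2a also lists Rifampin. Metamfetamine has 'No NDC', though the seizure-threshold row lists methamphetamine. Searching under one regional name would explain all of these, but that is an inference.

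**2. The phenytoin row**

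Many rows pair a plain code with a combination code in the same ATC group. Taking the last two digits, combination minus plain:

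| Drug | Plain | Combination | Difference |
|---|---|---|---|
| Quinidine | C01BA01 | C01BA51 | 50 |
| Cinnarizine | N07CA02 | N07CA52 | 50 |
| Dexchlorpheniramine | R06AB02 | R06AB52 | 50 |
| Dextropropoxyphene | N02AC04 | N02AC54 | 50 |
| Donepezil | N06DA02 | N06DA52 | 50 |
| Promethazine | R06AD02 | R06AD52 | 50 |
| Lidocaine | N01BB02 | N01BB52 | 50 |
| Palonosetron | A04AA05 | A04AA55 | 50 |
| Mephenytoin | N03AB04 | N03AB54 | 50 |
| Phenytoin | N03AB04 | N03AB52 | 48 |

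Two drugs share N03AB04. Mephenytoin fits the pattern of the eight rows above it and phenytoin does not: N03AB52 implies a plain code ending 52 − 50 = 02. On the protocol's own evidence, the phenytoin row is the faulty one.

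**3. What is lost and what is kept in the Nordic data**

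- Plain paracetamol: no CYP2D6 flag. Codeine, tramadol and oxycodone combinations with paracetamol are still found, because those opioid rows carry combination codes (N02AJ06 to 09, N02AJ13 to 16, N02AJ17 to 19) and all three opioids are on the CYP2D6 list.
- Pethidine: no CYP2B6-substrate or CYP2D6 flag from its row. These users still count as opioid users through class code N02A.
- Amphetamine and dextroamphetamine: no CYP2D6 flag, and no listed ATC code for the seizure-threshold variable either.
- Phenytoin: plain product missed, combinations still found through N03AB52. Phenytoin is listed as CYP2B6 inducer, CYP2B6 substrate and CYP2D6 drug, so three variables are touched.
- Mephenytoin: counted as phenytoin. Appendix 2a already lists it as a CYP2B6 substrate and CYP2D6 drug, so at class level these users wrongly gain only the inducer flag.

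**The case against.** Several points on the other side are sound.

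- A reader might infer that US-Nordic contrasts will be biased. Section 9.7.1 has all analyses done separately by country, section 9.4.2 puts the US results in a US-only report, and the planned synthesis is across the Nordic databases. No formal US-Nordic comparison is planned, so this does not hold as a bias in a planned analysis. The Nordic counts are still too low in themselves.
- A reader might infer that these users cannot be counted at all. The retained routes in the working show otherwise.
- A reader might extend the point to every 'No ATC' row. For rows such as regorafenib, methimazole or curcumin, only the ATC index could show an error. They need checking and no more.
- CYP and seizure-threshold drugs are not among the non-compliance criteria in sections 8 and 9.7.2. The contraindicated medicines (bupropion, naltrexone, MAOIs, opioids) all have ATC codes, so the compliance groups are untouched.
- The seizure-threshold row lacks NDC codes as well as ATC codes, so it creates no regional asymmetry. An analyst could also look up codes from the names there and in Appendix 2a.

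Two further defences are weaker. Section 9.3.3 leaves final definitions to the SAP, but an explicit wrong entry in a pre-specified list is likely to be carried forward. A digit in the phenytoin row could have been misread from the PDF, which is worth checking against the original, but that would not explain the four 'No ATC' entries.

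**Conclusion.** The point holds in limited form. Appendix 2 as written would understate Nordic use of CYP2D6 and CYP2B6 drugs and leave two amphetamines without any listed ATC code. It would also miss plain phenytoin and count mephenytoin as phenytoin. This affects the baseline description under primary objective 1 and the co-medication analyses in section 9.7.3.1.

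The size cannot be computed. If a share x of Nordic users take plain paracetamol and a share o of those are flagged by another listed CYP2D6 drug anyway, the understatement from that row is x(1 − o). The protocol gives neither x nor o. The CYP2D6 list is long and includes common antidepressants, beta-blockers and opioids, so the overlap could be large, and any percentage offered here would be a guess.

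The conclusion rests on two assumptions: that the paired names are synonyms, and that the analyst follows the list literally. It is worth correcting because the entries are visibly inconsistent and the repair is cheap. No headline estimate depends on it.

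**What to change.** Before the Nordic analysis:

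1. Re-search acetaminophen, amphetamine, dextroamphetamine and meperidine by international name and enter the ATC codes found.
2. Check the remaining 'No ATC' rows in the same way. Where there is truly no code, say so.
3. Reconcile N03AB04 between phenytoin and mephenytoin against the ATC index.
4. Add ATC codes to the seizure-threshold row.
5. Leave the US search unchanged, since Milestones scheduled the US final report for August 2023. State in the report any drug captured in only one region.

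The cost is a code-list edit and re-flagging. Section 9.6 already obtains all healthcare-transactional data for included patients, so no new data or patients are needed.
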